Appendix 5. International Working Group Criteria for AML {Cheson 2003}

Assessment of clinical response will be made according to the International Working Group criteria {Cheson 2003}. The major criteria for judging response will include physical examination and examination of blood and bone marrow. All laboratory studies that are abnormal prior to study will be repeated to document the degree of maximal response.

Early Treatment Assessment (ETA)

- Evaluation is made at approximately 7-10 days after completing the last dose of the initial course of treatment (ie, Group A Cycle 1 Day 14)
- Guides subsequent treatment (eg, need for or timing of second induction course)

Morphologic Leukemia-free State (MLFS)

MLFS requires all of the following:

- <5% blasts in bone marrow aspirate
- No extramedullary disease
- No blasts with Auer rods detected

Morphologic Complete Remission (CR)

CR requires all of the following:

- <5% blasts in bone marrow aspirate
- Neutrophils $\geq 1,000/\mu\text{L}$
- Platelets $\geq 100,000/\mu\text{L}$
- No extramedullary disease
- No blasts with Auer rods detected
- Independent of transfusions

Cytogenetic Complete Remission (CRc)

CRc requires all of the following:

- <5% blasts in bone marrow aspirate
- Neutrophils $\geq 1,000/\mu\text{L}$

- Platelets $\geq 100,000/\mu\text{L}$
- No extramedullary disease
- No blasts with Auer rods detected
- Independent of transfusions
- Reversion to a normal karyotype with an abnormal karyotype at the time of diagnosis

Morphologic CR with incomplete blood count recovery (CRi)

CRi requires all of the following:

- $< 5\%$ blasts in bone marrow aspirate
- Neutrophils $< 1,000/\mu\text{L}$ or Platelets $< 100,000/\mu\text{L}$
- No extramedullary disease
- No blasts with Auer rods detected

If blood counts recover within 14 days of a bone marrow evaluation that is consistent with CRi, the patient will be considered CR at the time when both neutrophil and platelet count recover (neutrophils $\geq 1,000/\mu\text{L}$, platelets $\geq 100,000/\mu\text{L}$).

Partial Remission (PR)

PR requires all of the following:

- $\geq 50\%$ decrease in blasts in bone marrow aspirate to a range of 5-25%
- Neutrophils $\geq 1,000/\mu\text{L}$
- Platelets $\geq 100,000/\mu\text{L}$
- Independent of transfusions
- A value of $\leq 5\%$ blasts may also be considered a PR if Auer rods are detected

Treatment Failure (TF)

Treatment failure will be classified as one of the following:

- Resistant disease: Failure to achieve a complete remission (CR, CRc, or CRi) or partial remission. Patients who survive ≥ 7 days following completion of initial treatment, with evidence of persistent leukemia by blood and/or bone marrow examination.

- Death in Aplasia: Patients who survive ≥ 7 days following completion of initial treatment, but die while cytopenic, with an aplastic or hypoplastic marrow obtained within 7 days of death, without evidence of persistent leukemia
- Death from Indeterminate cause: Patients who die before completion of treatment or < 7 days following completion of initial treatment; patients who die ≥ 7 days following completion of initial treatment with no peripheral blood blasts, but no bone marrow examination is available; patients who fail to complete the first cycle of therapy

Relapse

Relapse is defined as:

- Evidence of morphologic relapse with the reappearance of leukemic blasts in the peripheral blood, blasts with Auer rods, $\geq 5\%$ blasts in the bone marrow, or evidence of extramedullary disease not attributable to any other cause. In the setting of recent treatment, if there are no circulating blasts and the bone marrow contains 5-20% blasts, a bone marrow biopsy should be repeated within 1 week to distinguish relapse from bone marrow regeneration.
- The reappearance of cytologically proven extramedullary disease also indicates relapse. Reappearance of a cytogenetic abnormality is considered a cytogenetic relapse. Evidence of bone marrow morphologic involvement or extramedullary disease required.

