6. EFFICACY ANALYSES

Assessment of clinical response will be made according to the International Working Group criteria for AML {Cheson 2003}, which is documented in Appendix 5 of the study protocol. The major criteria for judging response assessment include physical examination and examination of blood and bone marrow.

Efficacy analysis will be presented by treatment group, phase, and dose level, treatment arm, or cohort if applicable, as elaborated in Table 3-2 in Section 3.2. In addition, the pooled analyses of Group C for efficacy specified in Sections 6.1, 6.2, and 6.3 will be present by dose level and total as elaborated in Table 3-3 in Section 3.2. Summaries will be provided for the FAS.

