6.1. Primary Efficacy Endpoints

6.1.1. Definition of the Primary Efficacy Endpoints

- Complete remission rate at induction completion: defined as the proportion of subjects who achieved morphologic complete remission (CR) at induction completion. Note that CR includes a subcategory of cytogenetic CR (CRc)
- Composite complete remission rate at induction completion: defined as the proportion of subjects who achieved morphologic complete remission (CR) or morphologic complete remission with incomplete blood count recovery (CRi) at induction completion
- Overall response rate at induction completion: defined as the proportion of subjects who achieved morphologic complete remission (CR), morphologic complete remission with incomplete blood count recovery (CRi), or partial remission (PR) at induction completion

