6.1.2. Analysis of the Primary Efficacy Endpoints

Complete remission rate, composite complete remission (CR/CRi) rate, and overall response (CR/CRi/PR) rate at induction completion for Groups A and B will be summarized and the corresponding 95% exact CIs based on Clopper-Pearson method will be presented.

Response at induction completion is defined as the best response across the time points that occurred after day 1 of last cycle of induction therapy, and prior to the earliest of cycle 1 day 1 of post-remission or maintenance therapy, date of SCT and date of other anticancer therapy (excluding SCT and conditioning regimen (listed in Appendix 2)). Best response is the best outcome according to the ranking below by decreasing favorable level:

- 1) Cytogenetic Complete Remission [CRc]
- 2) Morphologic Complete Remission [CR]
- 3) Morphologic Complete Remission with Incomplete Blood Count Recovery [CRi]

- 4) Partial Remission [PR]
- 5) Morphologic Leukemia-free State [MLFS]
- 6) Relapse
- 7) Other

The category “Other” includes 3 subcategories: Treatment Failure [TF], Early Treatment Assessment [ETA], and No Assessment Done. For subjects who had response assessment in the last cycle but didn’t achieve any of the first 6 categories listed above at induction completion, TF will be the response at induction completion for those who received 2 induction cycles in Group A or received ≥ 2 induction cycles in Group B, and ETA will be the response at induction completion for those who only received ≤ 1 induction cycle. All subjects in “Other” will be considered as nonresponders and will be included in the denominator when calculating the remission rates at induction completion.

Complete remission rate, composite complete remission (CR/CRi) rate, and overall response (CR/CRi/PR) rate per best overall response ever achieved during the treatment for Group C will be summarized and the corresponding 95% exact CIs based on Clopper-Pearson method will be presented.

Best overall response is defined as the best response across all time points prior to SCT and other anticancer therapy (excluding SCT and conditioning regimen). Best response is the best outcome according to the ranking below by decreasing favorable level:

- 1) Cytogenetic Complete Remission [CRc]
- 2) Morphologic Complete Remission [CR]
- 3) Morphologic Complete Remission with Incomplete Blood Count Recovery [CRi]
- 4) Partial Remission [PR]
- 5) Morphologic Leukemia-free State [MLFS]
- 6) Other

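### Appendix 5 handles transfusions inconsistently: a cleared marrow with recovered counts but continuing transfusions is MLFS only, and the 14-day CRi-to-CR sentence carries no transfusion condition

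*Protocol*

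**What the plan says.** Protocol Appendix 5 defines the response categories, and SAP Section 6 takes its response criteria from there: "which is documented in Appendix 5 of the study protocol".

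- **CR** has six requirements: under 5% marrow blasts, neutrophils of at least 1,000/µL, platelets of at least 100,000/µL, no extramedullary disease, no blasts with Auer rods, and "Independent of transfusions". CRc repeats all six and adds a karyotype item.
- **CRi** requires all of its items, one of which is neutrophils below 1,000/µL or platelets below 100,000/µL. It has no transfusion item.
- **PR** needs at least a halving of blasts to 5-25% (or a value of 5% or less with Auer rods), both counts recovered, and transfusion independence.
- **MLFS**: "MLFS requires all of the following", followed by only three items, on blasts, extramedullary disease and Auer rods.
- **14-day rule**: if counts recover within 14 days of a marrow consistent with CRi, "the patient will be considered CR at the time when both neutrophil and platelet count recover". Only the two count thresholds are named.

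SAP 6.1.1 and 6.1.2 build the three primary rates from CR, CR/CRi and CR/CRi/PR. MLFS is ranked fifth, below PR. For EFS, SAP 6.2.2 treats as a failure any subject who was assessed but never scored CRc, CR, CRi or PR before transplant or other anticancer therapy.

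**The concern.** Transfusion independence is a condition for CR, but failing it is not a route into CRi. A subject who misses CR on that item alone therefore skips CRi and falls to MLFS. Better counts then give a worse score: recovering the second count while still transfused moves a subject out of the definition of CRi. The 14-day sentence works in the opposite direction, since it can give CR with the transfusion item unmet.

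The two faults touch different results. The first lowers the composite and overall rates and can add an EFS event. The second can raise the CR rate but leaves the composite and overall rates alone, because the subject was already CRi.

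**Working it through.** **1. The plan's own figures for the affected endpoint.** Protocol Table 8-1 gives exact 90% intervals for the composite rate at n=40. The Clopper-Pearson limits are the 5% quantile of Beta(x, n−x+1) and the 95% quantile of Beta(x+1, n−x).

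| x/n | Computed | Plan |
|---|---|---|
| 28/40 (70%) | 56.0-81.7 | 56-82 |
| 32/40 (80%) | 66.8-89.6 | 67-90 |
| 36/40 (90%) | 78.6-96.5 | 79-97 |
| 10/20 (50%, Group B arm) | 30.2-69.8 | 30-70 |

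All reproduce. The concern is with the definitions and leaves these tables unchanged.

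**2. Appendix 5 applied literally.** Fix under 5% blasts, no Auer rods and no extramedullary disease, so PR is not available and MLFS is always met. Four yes/no items remain: neutrophils recovered, platelets recovered, transfusion-independent, and a CRi marrow in the previous 14 days. That makes 2×2×2×2 = 16 states.

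| Counts | Transfused? | CRi marrow in previous 14 days? | States | Best category met |
|---|---|---|---|---|
| At least one low | either | either | 3×2×2 = 12 | CRi |
| Both recovered | no | either | 2 | CR |
| Both recovered | yes | yes | 1 | CR, by the 14-day sentence only |
| Both recovered | yes | no | 1 | MLFS only |

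Exactly one state is MLFS only. As an example, neutrophils of 1,500/µL and platelets of 120,000/µL with red cells still transfused is MLFS; the same subject with platelets of 95,000/µL is CRi. The last two rows are the same clinical state on the day, scored CR or MLFS according to whether a CRi marrow came first.

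**3. Carrying this to the endpoints.** For Groups A and B, SAP 6.1.2 takes the best response after Day 1 of the last induction cycle and before the next phase, transplant or other therapy. An MLFS-only subject stays in the denominator and is in no numerator. CR is rightly missed under the definition, so the loss falls on the composite and overall rates. If no assessment before transplant or other therapy is better than MLFS, the subject is a treatment failure under SAP 6.2.2, and an EFS event if the assessment window in SAP Table 6-1 is met.

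**4. Size per subject.** One subject is 1/40 = 2.5 points in Group A Phase 2 and 1/20 = 5 points in a planned Group B arm. SAP Section 1 says Group B Phase 2 closed before its planned size; in an arm smaller than 20, each subject counts for more than 5 points. The number affected, k, is not in the documents. Taking k = 0 to 3 purely as an assumption:

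| k | From 28/40 (90% CI) | From 10/20 (90% CI) |
|---|---|---|
| 0 | 70.0% (56.0-81.7) | 50.0% (30.2-69.8) |
| 1 | 67.5% (53.4-79.6) | 45.0% (25.9-65.3) |
| 2 | 65.0% (50.8-77.4) | 40.0% (21.7-60.6) |
| 3 | 62.5% (48.3-75.3) | 35.0% (17.7-55.8) |

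**The case against.** **Best response protects many subjects.** This stands. Group A has a marrow at Cycle 1 Day 14, which protocol 3.1.2 describes as the count nadir. On the literal bullets, a cleared marrow with low counts is already CRi, and a later transfused marrow cannot lower it. Group A loss is then largely confined to subjects whose Day-14 marrow was not cleared or not evaluable. How fully this protects them depends on sites scoring that marrow as a response, since Appendix 5 also names it as the early treatment assessment. Group B, with scheduled induction marrows at the end of Cycles 2 and 4, is more exposed.

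**The 14-day sentence may only fix timing.** It can be read as saying when a CRi becomes CR, with every other CR item still in force. That reading is possible. A reader might infer that the sentence plainly waives the transfusion item, but the text is silent. It permits the error without requiring it, which is reason enough to align it.

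**Frequency is unknown.** This stands. A reader might infer a loss of several points because protocol 7.1.2.1 says transfusion support will be needed. That statement concerns AML at initial diagnosis or relapse. It says nothing about cleared marrows with recovered counts. Appendix 5 also names no blood product and no transfusion-free period, so the gap cannot be sized.

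**Changing CRi late favors the drug.** This also stands. The study is open-label, enrollment had been completed or terminated when the SAP was written, and a wider CRi can only raise the composite and overall rates. It is a reason to report results both ways.

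**Consequences are limited.** The analyses are descriptive, the Cohort C1A futility decision has been made, and SAP Section 1 reports a lack of responses to monotherapy. This lowers the stakes, mostly for Group C. The Group A and B rates remain primary endpoints.

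**Conclusion.** The inconsistency is real on the text as written and reaches the primary endpoints. One state is left as MLFS only, although the same subject with a low count would be CRi. The 14-day sentence can also credit CR to a subject who does not meet the CR definition. The first part rests on the CR transfusion item set against the CRi count item, and applies only when no CRi was scored earlier in the response window.

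The supportable size is 2.5 points per subject at n=40 and 5 points at n=20. No total can be given.

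A reader might infer that the SAP formally labels these subjects nonresponders. It uses that word only for its category Other (treatment failure, early treatment assessment, no assessment). MLFS subjects are excluded from the numerators in effect, and can be treatment failures for EFS. Nor does the finding imply that the sample-size tables are wrong; they reproduce.

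**What to change.** 1. In the Appendix 5 14-day sentence, add transfusion independence as a condition, so that an upgraded CR meets the CR definition.
2. In SAP 6.1.2, before database finalization, state that a subject who meets every CR criterion except transfusion independence is scored CRi. Define transfusion independence once, by blood product and time window, and apply that definition to all subjects.
3. Report the composite and overall rates and EFS with and without the subjects reclassified under item 2, because that rule departs from the criteria as transcribed in Appendix 5 and can only raise the two rates.
4. Check recorded responses against the transfusion listing already planned in SAP 7.6.

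The cost is a few sentences, one programmed check on transfusion, hematology and marrow data already collected, and one sensitivity table. A few upgraded CRs may revert to CRi, which would lower the CR rate. No sample-size figure changes.

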Appendix 6. Performance Scales: Karnofsky & ECOG Scores {Oken 1982}

Karnofsky Status	Karnofsky Grade	ECOG Grade	ECOG Status
Normal, no complaints	100	0	Fully active, able to carry on all pre-disease performance without restriction
Able to carry on normal activities. Minor signs or symptoms of disease	90	0	Fully active, able to carry on all pre-disease performance without restriction
Normal activity with effort	80	1	Restricted in physically strenuous activity but ambulatory and able to carry out work of a light or sedentary nature, eg, light house work, office work
Care for self. Unable to carry on normal activity or to do active work	70	1	Restricted in physically strenuous activity but ambulatory and able to carry out work of a light or sedentary nature, eg, light house work, office work
Requires occasional assistance, but able to care for most of his needs	60	2	Ambulatory and capable of all selfcare but unable to carry out any work activities. Up and about more than 50% of waking hours
Requires considerable assistance and frequent medical care	50	2	Ambulatory and capable of all selfcare but unable to carry out any work activities. Up and about more than 50% of waking hours
Disabled. Requires special care and assistance	40	3	Capable of only limited selfcare, confined to bed or chair more than 50% of waking hours
Severely disabled. Hospitalisation indicated though death nonimminent	30	3	Capable of only limited selfcare, confined to bed or chair more than 50% of waking hours
Very sick. Hospitalisation necessary. Active supportive treatment necessary	20	4	Completely disabled. Cannot carry on any selfcare. Totally confined to bed or chair
Moribund	10	4	Completely disabled. Cannot carry on any selfcare. Totally confined to bed or chair
Dead	0	5	Dead

Appendix 7. Minimal Residual Disease (MRD) Level Definition {Sanchez-Garcia 2013}

MRD Level (by flow cytometry)	% of Leukemia Cells
No Measurable	≤ 0.01
Low	> 0.01 and ≤ 0.1
Intermediate	> 0.1 and ≤ 1
High	> 1

Appendix 8. 2017 European Leukemia Network (ELN) Risk Stratification by Genetics^a {Dohner 2017}

Risk Category	Genetic Abnormality
Favorable	t(8;21)(q22;q22.1); RUNX1-RUNX1T1 inv(16)(p13.1q22) or t(16;16)(p13.1;q22); CBFB-MYH11 Mutated NPM1 without FLT3-ITD or with FLT3-ITD ^{low(c)} Biallelic mutated CEBPA
Intermediate	Mutated NPM1 and FLT3-ITD ^{high(c)} Wild type NPM1 without FLT3-ITD or with FLT3-ITD ^{low(c)} (w/o adverse risk genetic lesions) t(9;11)(p21.3;q23.3); MLL3-KMT2A ^d Cytogenetic abnormalities not classified as favorable or adverse
Adverse	t(6;9)(p23;q34.1); DEK-NUP214 t(v;11q23.3); KMT2A rearranged t(9;22)(q34.1;q11.2); BCR-ABL1 inv(3)(q21.3q26.2) or t(3;3)(q21.3;q26.2); GATA2,MECOM(EV11) -5 or del(5q); -7; -17/abn(17p) Complex karyotype, ^e monosomal karyotype ^f Wild type NPM1 and FLT3-ITD ^{high(c)} Mutated RUNX1 ^g Mutated ASXL1 ^g Mutated TP53 ^h

- a Frequencies, response rates and outcome measures should be reported by risk category, and, if sufficient numbers are available, by specific genetic lesions indicated.
- b Prognostic impact of a marker is treatment-dependent and may change with new therapies.
- c Low, low allelic ratio (<0.5); high, high allelic ratio (>0.5); semi-quantitative assessment of *FLT3-ITD* allelic ratio (using DNA fragment analysis) is determined as ratio of the area under the curve (AUC) “*FLT3-ITD*” divided by AUC “*FLT3-wild type*”; recent studies indicate that acute myeloid leukemia with *NPM1* mutation and *FLT3-ITD* low allelic ratio may also have a more favorable prognosis and patients should not routinely be assigned to allogeneic hematopoietic-cell transplantation.
- d The presence of t(9;11)(p21.3;q23.3) takes precedence over rare, concurrent adverse-risk gene mutations.
- e Three or more unrelated chromosome abnormalities in the absence of one of the World Health Organization-designated recurring translocations or inversions, ie, t(8;21), inv(16) or t(16;16), t(9;11), t(v;11)(v;q23.3), t(6;9), inv(3) or t(3;3); AML with *BCR-ABL1*.
- f Defined by the presence of one single monosomy (excluding loss of X or Y) in association with at least one additional monosomy or structural chromosome abnormality (excluding core-binding factor AML).
- g These markers should not be used as an adverse prognostic marker if they co-occur with favorable-risk AML subtypes.
- h *TP53* mutations are significantly associated with AML with complex and monosomal karyotype.

DLT	dose limiting toxicity
ECG	electrocardiogram
ECOG	Eastern Cooperative Oncology Group
EFS	event free survival
ELN	European LeukemiaNet
ENTO	Entospletinib, GS-9973
EOS	end of study
ETA	early treatment assessment
FAB	French-American-British
FISH	fluorescent in situ hybridization
HLT	high-level term
HOXA9	Homeobox A9
ID	identification
IWRS	Interactive Web Response System
IV	intravenous
KM	Kaplan-Meier
LLT	lower-level term
LOQ	limit of quantitation
MedDRA	Medical Dictionary for Regulatory Activities
MEIS1	Myeloid Ecotropic Viral Integration Site 1
MLFS	morphologic leukemia free state
MLL	mixed lineage leukemia
MRD	minimal residual disease
MTD	maximum tolerated dose

OS	overall survival
PK	pharmacokinetic(s)
PR	partial remission
PT	preferred term
Q1	first quartile
Q3	third quartile
RFS	relapse - free survival
R/R	relapsed/refractory
SAP	statistical analysis plan
SAE	serious adverse event
SCT	stem cell transplant
SOC	system organ class
StD	standard deviation
TEAE	treatment-emergent adverse event
TF	treatment failure
TFLs	tables, figures, and listings
WBC	white blood cell
WHO	World Health Organization

1. INTRODUCTION

This statistical analysis plan (SAP) describes the statistical analysis methods and data presentations to be used in tables, figures, and listings (TFLs) in the clinical study report (CSR) for Study GS-US-339-1559. This SAP is based on the study protocol amendment 7 dated 15 February 2018 and the electronic case report form (eCRF). This study was intended to evaluate the efficacy, safety, and tolerability of entospletinib (ENTO) in subjects with Acute Myeloid Leukemia (AML). Due to the lack of responses to ENTO monotherapy and the evolving treatment landscape for AML, the recruitment of Group B Phase 2 was permanently closed prior to the planned sample size being reached. The enrollments of other treatment groups/cohorts were either completed or terminated, and, as such, this study will be terminated early. The SAP will be finalized before database finalization. Any changes made after the finalization of the SAP will be documented in the CSR.

1.1. Study Objectives

The primary objectives of this study are as follows:

- To demonstrate the overall safety of ENTO in combination with standard dose cytarabine and daunorubicin chemotherapy (7+3) in subjects with previously untreated AML who are candidates for chemotherapy (fit subjects) and to assess the efficacy of ENTO at the recommended Phase 2 dose (RP2D) (Group A)
- To demonstrate the overall safety of ENTO in combination with hypomethylating agents (decitabine or azacitidine) in subjects with previously untreated AML who are not candidates for 7+3 (unfit subjects) and to assess the efficacy of ENTO at the RP2D (Group B)
- To demonstrate the overall safety of ENTO monotherapy in subjects with previously untreated AML who are not candidates for chemotherapy or in subjects with relapsed/refractory (R/R) AML with or without mixed-lineage leukemia (MLL) and to assess the efficacy of ENTO at the RP2D (Group C)

The secondary objectives of this study are as follows:

- To assess the qualitative and quantitative toxicities of ENTO monotherapy or ENTO in combination with chemotherapy in subjects with AML
- To document therapeutic response of subjects with AML treated with ENTO monotherapy or ENTO in combination with chemotherapy

The exploratory objective of this study is as follows:

- **CCI** [REDACTED]

